### **4.4. Estimated Duration of Subject Participation and Follow-up**

Subjects will be followed for up to 20 weeks (including the screening period). If a subject completes the study with an ongoing AE, the site will continue to follow up with the subject for 30 days from the study completion date, until resolution is reached and documented. If, after 30 days, the AE is still continuing but not assessed as serious, the outcome will be recorded as ongoing and no further follow-up will be necessary. If a subject completes the study with an ongoing SAE, the subject will be followed until resolution or stabilization (i.e., the AE returns to baseline, can be attributed to agents other than the study device, or to factors unrelated to the study conduct; or no further follow-up is deemed necessary by the Investigator or it becomes unlikely that any additional information can be obtained).

#### **4.5. Interim Analysis**

An administrative extract of the data on September 2, 2016 will be used to tabulate the data for the post-operative patients. This tabulation is being prepared for a regulatory filing and does not constitute a formal analysis.

## 5. SCHEDULE OF ASSESSMENTS

Period	Screening Visit	Enrollment (Baseline) Visit 	Treatment Period	Interim Visits	End of Treatment Visit
Study Day	-14 to 0	0	As Prescribed	As Prescribed	As Prescribed
Informed Consent	X				
Demographic Information	X				
Medical/Surgical History	X				
Urine Pregnancy Test 	X				
Height and Weight	X				X 
Inclusion/Exclusion Criteria	X	X			
Efficacy Outcomes Assessments		X		X	X
Study Device Training		X 			
Dispense Study Device		X			
Distribute Diary Collection Tool(s)		X 			
Study Device Treatment			X 		
Assess Adverse Events and Concomitant Medications	X 	X		X	X
Assess Subject Adherence to Treatment				X	X
Collect Diary Collection Tool(s)				X	X
Return Study Device and Unused DACs					X 

1. The Screening Visit and the Enrollment Visit may occur on the same day in which case none of the screening tests need to be repeated.
2. Urine pregnancy test will be performed on women of child-bearing potential.
3. Introduction to and training on the study device will be completed during the Enrollment Visit.
4. Distribution of a diary collection tool will occur if the investigator decides to use this as a means for capturing patient reported outcomes. Completion of the forms will occur as instructed by the investigative site, as applicable.
5. The subject will self-administer treatments as prescribed by the investigator.
6. Collect only weight at End of Treatment Visit.
7. Assessment of adverse events will be conducted after the signing of the Informed Consent.
8. At the End of Treatment Visit subjects will return the study device and all unused Disposable Applicator Covers (DACs).

## 6. ANALYSIS POPULATIONS

The results from this study will be presented using a single population.

- **ITT / Safety Population:** All subjects who are consented and treatment with the study device is initiated, independent of the treatment being successful implemented.

## 7. ANALYSIS CONVENTIONS

Post-text tables and listings will be prepared in accordance with the current ICH Guidelines. The header of each table and listing will include the sponsor’s name and the study number. The information and explanatory notes to be provided in the “footer” or bottom of each table and listing will include the following information:

1. Date and time of output generation.
2. SAS® program name, including the path that generates the output.
3. Any other output specific details that require further elaboration.

In general, tables will be formatted with a column displaying findings for all subjects combined. Row entries in tables are made only if data exist for at least one subject (*i.e.*, a row with all zeros will not appear). The only exception to this rule applies to tables that list the termination status of subjects (*e.g.*, reasons for not completing the study). In this case, zeros will appear for study termination reasons that no subject satisfied. The summary tables clearly indicate the number of subjects to which the data apply and unknown or not performed are distinguished from missing data. Tables, listings, and figures will provide the units of measurement, unless not applicable.

Quantitative results recorded multiple times over the course of the study will be presented using the *Level 1* display.

Baseline Parameters	Reason for Study Enrollment: Pain	Reason for Study Enrollment: Edema	Reason for Study Enrollment: Pain and Edema	Overall
Age 
 
● N
 
● Mean
 
● Standard Deviation
 
● Median
 
● Minimum, Maximum Values
 
● Inter-Quartile Range (IRQ)
 
				
Gender 
 
● Male (N [%])
 
● Female (N [%])
 
				

The *Level 2* display will be used for summarizing response by Reason for Study Enrollment (Pain, Edema or Pain and Edema). An example of the layout is presented below.

Evaluation Time Point	Reason for Study Enrollment: Pain	Reason for Study Enrollment: Edema	Reason for Study Enrollment: Pain and Edema	Overall
Baseline Pain Score 
 
● N
 
● Mean
 
● Standard Deviation
 
● Median
 
● Minimum, Maximum Values
 
● Inter-Quartile Range (IRQ)
 
				
Last Recorded Pain Score During the First 4 weeks on Study (Study Day 1 through Study Day 28) 
 
● N
 
● Mean
 
● Standard Deviation
 
● Median
 
● Minimum, Maximum Values
 
● Inter-Quartile Range (IRQ)
 
				
Last Recorded Pain Score During the First 4 weeks on Study (Study Day 1 through Study Day 28) minus Baseline 
 
● N
 
● Mean
 
● Standard Deviation
 
● Median
 
● Minimum, Maximum Values
 
● Inter-Quartile Range (IRQ)
 
				
Last Recorded Pain Score During the Study 
 
● N
 
● Mean
 
● Standard Deviation
 
● Median
 
● Minimum, Maximum Values
 
● Inter-Quartile Range (IRQ)
 
				
Last Recorded Pain Score During the Study (Final Score) minus Baseline 
 
● N
 
● Mean
 
● Standard Deviation
 
● Median
 
● Minimum, Maximum Values
 
● Inter-Quartile Range (IRQ)
 
				
Outcome Assessment Score 
 
● N
 
● Mean
 
● Standard Deviation
 
● Median
 
● Minimum, Maximum Values
 
● Inter-Quartile Range (IRQ)
 
				
Last Recorded Outcome Assessment				

Score During the First 4 weeks on Study (Study Day 1 through Study Day 28) 
 
• N
 
• Mean
 
• Standard Deviation
 
• Median
 
• Minimum, Maximum Values
 
• Inter-Quartile Range (IRQ)
 
				
Last Recorded Outcome Assessment Score During the First 4 weeks on Study (Study Day 1 through Study Day 28) minus Baseline 
 
• N
 
• Mean
 
• Standard Deviation
 
• Median
 
• Minimum, Maximum Values
 
• Inter-Quartile Range (IRQ)
 
				
Last Recorded Outcome Assessment Score During the Study 
 
• N
 
• Mean
 
• Standard Deviation
 
• Median
 
• Minimum, Maximum Values
 
• Inter-Quartile Range (IRQ)
 
				
Last Recorded Outcome Assessment Score During the Study (Final Score) minus Baseline 
 
• N
 
• Mean
 
• Standard Deviation
 
• Median
 
• Minimum, Maximum Values
 
• Inter-Quartile Range (IRQ)
 
				

The *Level 3* display will be used for summarizing the adverse events recorded through the course of the study. An example of the layout is presented below.

Adverse Events	Reason for Study Enrollment: Chronic or Acute Pain	Reason for Study Enrollment: Edema	Reason for Study Enrollment: Chronic or Acute Pain and Edema	Overall
System Organ Class				
Preferred Term				
Severity				

Supportive individual subject data listings will be sorted and presented by subject number and visit or diary entry date. Listings will also include the number of days relative to the initial study device treatment.

Specific algorithms are discussed for imputing missing or partially missing dates, if deemed appropriate, under specific data topics. Imputed or derived data will be flagged in the individual subject data listings. Imputed data will not be incorporated into any raw or primary datasets. The imputed data will be retained in the derived / analysis datasets.

The total duration for a subject *on-study* will be calculated as the difference between the date of initial study treatment and the last day of observation plus 1 day. All calculations for defining the duration on-study will follow the algorithm  $DURATION = [STUDY\ COMPLETION\ OR\ WITHDRAW\ DATE - INITIAL\ TREATMENT\ DATE + 1]$ .

This section details general conventions to be used for the statistical analyses. The following conventions will be applied to all data presentations and analyses.

- Summary statistics will consist of the count and percentage in each level for categorical variables, and the sample size (n) mean, median, standard deviation (SD), minimum, and maximum values for continuous variables.
- All mean and median values will be formatted to one more decimal place than the measured value. Standard deviation values will be formatted to two more decimal places than the measured value. Minimum and maximum values will be presented with the same number of decimal places as the measured value.
- The number and percentage of responses will be presented in the form XX (XX.X%).
- No formal hypothesis tests are planned for this clinical investigation. Probability values may be derived for informational purposes. All probability values will be rounded to four decimal places. All p-values that round to 0.0000 will be presented as '<0.0001' and p-values that round to 1.0000 will be presented as '>0.9999'. P-values <0.05 will be considered to be statistically significant.
- All summary tables will include the analysis population sample size (i.e., number of subjects).
- Study Day 1 is defined as the day the subject receives their initial exposure to the study device. All *study days* are determined relative to the day of initial treatment with the study device.
- Baseline values will be defined as those values recorded closest to, but prior to, the first study treatment.
- Change from baseline will be calculated as follows:
  - $Change = Post\text{-}baseline\ value - baseline\ value.$
- Date variables will be formatted as DDMMYYYY for presentation.
- Tables, figures, and listings will be presented in landscape orientation.

- SAS® Version 9.2 or higher will be the statistical software package used for all data analyses.
- All data from this study will be presented in listings. All listings will be sorted by subject number and visit date, as applicable.
- Table and listing numbering will follow ICH guidelines for post-text table and listing numbering.

### **7.1. Adjustments for Covariates**

The analyses will be adjusted using the baseline results to increase the precision of the estimates; the underlying assumption for inclusion of the covariate will be examined. Unadjusted analyses will also be conducted and reported.

### **7.2. Handling of Dropouts or Missing Data**

Missing data may have an impact upon the interpretation of the trial data. Values for missing data will not be imputed, however a tabulation of the last recorded observations will be performed. All available data for subjects who do not complete the study will be included in data listings.

### **7.3. Multiple Comparison/Multiplicity**

No adjustment for multiplicity will be applied, given there is no formal hypothesis that will be tested.

### **7.4. Examination of Subgroups**

Results will be evaluated relative to the condition the subject is using the study device to treat.

## 8. SUBJECT ACCOUNTING AND STUDY DISPOSITION

A complete accounting of subject participation in the study will be presented in Table 14.1.1 entitled *Subject Accounting and Final Study Disposition*. The Level 1 table layout will be used to present these results. The purpose of this table is to provide an accounting of subjects from their entrance into the study through the final visit and to account for subject evaluation in major analyses of safety and tolerability, including reasons for early study termination. The table will display the number of subjects who were screened and the number and percentage of subjects who:

- were enrolled
- are included in the Safety / ITT population
- completed the study
- discontinued the study

Listing 16.2.1 entitled *Subject Disposition* supports Table 14.1.1. This listing will be sorted by subject number and will contain the last study visit attended.

## **9. BASELINE SUBJECT DATA**

### **9.1. Baseline Demographic Factors**

All subjects in the Safety population will be included in Table 14.1.2 entitled *Baseline Demographics and Subject Characteristics*. The Level 1 table layout will be used to present these results. This table summarizes the subject population with respect to gender, age in years at the time of entry into the study, race, ethnicity, height (cm), weight (lbs) and calculated body mass index (BMI). Age, height, weight, and BMI will be summarized using descriptive statistics. The number and percent of each gender, race, and ethnicity category will be presented using counts and percentages. The supportive data for Table 14.1.2 will be presented in Listing 16.2.2 entitled *Subject Demographics*. This listing will be sorted by subject number.

### **9.2. Medical History**

The medical history for each subject and summarized in Table 14.1.3 entitled *Summary of Medical History*. The Level 1 table layout will be used to present these results. The subjects will be summarized using counts and percentages for those subjects who had a pre-study medical history. The supportive data for this table will be presented in Listing 16.2.3 entitled *Medical History*. This listing will be sorted by subject.

### **9.3. Outcome Assessments**

The data recorded on the Outcome Assessments case report form will be summarized in Table 14.1.4 entitled *Summary of Baseline Outcome Assessments*. The Level 1 table layout will be used to present these results. The subjects will be summarized using counts and percentages for each qualitative question. The supportive data for this table will be presented in Listing 16.2.4 entitled *Baseline Outcome Assessments*. This listing will be sorted by subject.

### **9.4. Baseline Pain Site Assessment**

The data recorded on the Baseline Pain Assessment case report form will be summarized in Table 14.1.5 entitled *Summary of Baseline Pain Assessment*. The Level 1 table layout will be used to present these results. The subjects will be summarized using counts and percentages for each qualitative question. The supportive data for this table will be presented in Listing 16.2.5 entitled *Baseline Pain Assessment*. This listing will be sorted by subject.

### **9.5. Baseline Edema Assessment**

The data recorded on the Baseline Edema Assessment case report form will be summarized in Table 14.1.6 entitled *Summary of Baseline Edema Assessment*. The Level 1 table layout will be used to present these results. The subjects will be summarized using counts and percentages for each qualitative question. The supportive data for this table will be presented in Listing 16.2.6 entitled *Baseline Edema Assessment*. This listing will be sorted by subject.

## **9.6. Baseline Wound Assessment**

The data recorded on the Baseline Wound Assessment case report form will be summarized in Table 14.1.7 entitled *Summary of Baseline Wound Assessment*. The Level 1 table layout will be used to present these results. The subjects will be summarized using counts and percentages for each qualitative question. The supportive data for this table will be presented in Listing 16.2.7 entitled *Baseline Wound Assessment*. This listing will be sorted by subject.

## 10. STUDY DEVICE ACCOUNTABILITY AND TREATMENT

This section will describe the summarization and analysis of the administration of the treatment with the Provant device.

### 10.1. Treatment Administration and Accountability

A summary of Provant treatment regimen will be presented in Table 14.2.1 entitled *Summary of the Provant Treatment Regimen (ITT / Safety Population)*. The frequency of treatment and length of the individual treatment sessions will be summarized using counts and percentages. Listing 16.2.8 entitled *Study Device – Application and Accountability* will contain all of the recorded treatment information; this listing will be sorted by subject number.

### 10.2. Interim Visit Outcome Assessments

#### 10.2.1. Description of the Data for Analysis

Data collected from the Outcome Assessments, Pain Intensity Assessment (Average), and Edema Assessment will be summarized. Results will be summarized in the following tables. Continuous variables will be summarized using descriptive statistics; categorical variables will be summarized using counts and percentages. Results will be presented using the Level 2 displays.

Table 14.4.1.1 Summary of the Interim Outcome Assessments (ITT / Safety Population)

Table 14.4.1.2 Summary of the Interim Pain Intensity Assessment (ITT / Safety Population)

Table 14.4.1.3 Summary of the Interim Edema Assessments (ITT / Safety Population)

The supportive data for these tables will be presented in Listing 16.2.9 entitled *Outcome Assessment*; Listing 16.2.10 entitled *Pain Intensity Assessment*; Listing 16.2.11 entitled *Final Edema Assessment*; These listings will be sorted by subject and relative day the measurements were recorded.

### 10.3. End of Study Assessments

#### 10.3.1. Description of the Data for Analysis

The last intra-subject data collected from the Outcome Assessments, Pain Intensity Assessment (Average), and Edema Assessment will be summarized. Results will be summarized in the following tables. Continuous variables will be summarized using descriptive statistics; categorical variables will be summarized using counts and percentages. Results will be presented using the Level 2 displays.

Table 14.4.2.1 Summary of the Final Outcome Assessments (ITT / Safety Population)

Table 14.4.2.2 Summary of the Final Pain Intensity Assessment (ITT / Safety Population)

Table 14.4.2.3 Summary of the Final Edema Assessments (ITT / Safety Population)

The supportive data for these tables will be presented in Listing 16.2.9 entitled *Outcome Assessment*; Listing 16.2.10 entitled *Pain Intensity Assessment*; Listing 16.2.11 entitled *Final Edema Assessment*; These listings will be sorted by subject and relative day the measurements were recorded.

## 11. SAFETY

The following sections describe how the safety endpoints will be analyzed.

### 11.1. Adverse Events

#### 11.1.1. Missing and Partial Adverse Event Dates

The start dates for AEs are important for the:

1. Treatment emergent algorithm.
2. The designation of unique AE occurrences.

Completely missing or partially missing adverse event onset dates will be imputed as follows after due diligence to obtain accurate adverse event information has failed.

If the AE start date is completely missing then the AE will be considered treatment-emergent unless it can be determined that the AE end date occurred prior to the start of the study. If this is the case, the AE will not be considered treatment-emergent.

If the adverse event start date is partially missing and the partial date is not sufficient to determine if the event occurred after the start of the study, then the AE will be considered treatment-emergent unless it can be determined that the AE end date occurred prior to the start of the study.

#### 11.1.2. Summaries of Adverse Events

All summaries of AEs will be based on treatment-emergent AEs and presented using the Level 3 table designs. Adverse events will be mapped to preferred terms and body systems using the Medical Dictionary for Regulatory Activities (MedDRA) coding dictionary version 18.1. The number and percentage of subjects experiencing AEs will be summarized by system organ class and preferred term. Summaries by maximum severity and relationship to the study device will also be provided. Serious adverse events and AEs leading to discontinuation from the study will be presented by system organ class and preferred term.

##### 11.1.2.1. Summary of Adverse Events by System Organ Class and Preferred Term

Table 14.3.1.1 entitled *Summary of Adverse Events by System Organ Class and Preferred Term* contains the primary presentation of the AE data. This table is prepared without regard to causality or relationship to the study device. Subjects will be counted only once at the system organ class level and will be counted once for each applicable preferred term; multiple occurrences of the same preferred term for a subject within a period will be counted only once. The number and percentage of subjects experiencing each system organ class and preferred term will be displayed by treatment. System organ classes, and preferred terms within system organ class, will be displayed alphabetically. The incidence of AEs will be summarized using counts and percentages.

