Adverse events will be mapped to preferred terms and body systems using the Medical Dictionary for Regulatory Activities (MedDRA) coding dictionary. While the primary presentation of adverse events will be subject-based, the number of adverse events will also be reported. The number and percentage of subjects reporting each event will be summarized. Incidence of adverse events by maximum reported severity will also be tabulated. Serious adverse events and adverse events leading to discontinuation will be displayed.

D. Eligibility Criteria

Eligibility for participation in this study will be based on the inclusion/exclusion criteria. An individual subject may only be included in the study once.

1. Inclusion Criteria

1. Subject age is greater than or equal to 22 years.
2. Subject has pain (chronic or acute) and/or edema that the prescriber deems treatment with Provant is warranted.

3. Subject is willing and able to give written informed consent.
4. Female subjects must be post-menopausal, surgically sterile, abstinent, or practicing (or agree to practice) an effective method of birth control if they are sexually active for the duration of the study. (Effective methods of birth control include prescription hormonal contraceptives, intrauterine devices, double-barrier methods, and/or male partner sterilization).

2. Exclusion Criteria

1. Subject requires or anticipates the need for surgery of any type during the duration of treatment.
2. Subject has received any investigational drug or device within 30 days or 5 half-lives of the drug, whichever is longer, prior to the Screening Visit or is enrolled in another clinical trial.
3. Subject has used systemic corticosteroids within 2 months of the Screening Visit.
4. Subject has a history of a solid tumor that is not in complete remission for greater than 2 years other than successfully treated non-metastatic basal cell or squamous cell carcinomas of the skin in the treatment area.
5. Subject has a history of blood cancer (e.g., leukemia, lymphoma, multiple myeloma).
6. Subject has a serious psychosocial co-morbidity.
7. Subject has a history of drug or alcohol abuse within one year prior to the Screening Visit.
8. Subject has an implanted pacemaker, defibrillator, neurostimulator, spinal cord stimulator, bone stimulator, cochlear implant, or other implanted device with an implanted metal lead(s).
9. Subject is currently pregnant or planning on becoming pregnant during the treatment period.

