Subjects will return to the clinic after completion of treatment as required by the study investigator. At this visit, the following procedures will be performed:

1. Collect subject's weight
2. Review and record adverse events
3. Review and record all concomitant medications
4. Conduct efficacy assessments:

Response to treatment with Provant will be determined based on the location of the subject's treatment area. Assessments will include the NPRS, CGI-I, PGIC and non-invasive assessments part of the Investigators standard of practice e.g., pain scores, SF-36, ankle-foot scales, oxygen perfusion (MOXY), and diaries with some subjects.

5. Return of study device and unused DACs
6. Return of the patient reported outcome form(s), as applicable. Examples of diary collection tools are provided in Appendix B.

F. Post-treatment Phone Call

Three months after the End of Treatment Visit, subjects will be contacted via telephone and asked to rate their pain using the NPRS.

G. Treatment adherence/study compliance

Subject adherence (compliance with the prescribed treatment regimen) will be assessed during interim visits and upon completion of the treatment period by the research staff reading and recording the number displayed on the study device usage meter. The usage meter will read 0.0 when dispensed. A subject with complete adherence will be expected to have a usage meter reading of 1.0 for each hour of treatment.

Subjects will be instructed to return any unused DACs at the End of Treatment visit. Compliance will be assessed by counting the number of returned, unused DACs, and subtracting this from the total number of DACs dispensed (120). As each treatment session requires one new DAC, compliance can be calculated based on the number of returned DACs relative to the prescribed regimen.

H. Protocol Adherence

If protocol modifications are necessary, all alterations that are not solely of an administrative nature require a formal protocol amendment.

If an investigator has deviated from the protocol in order to eliminate an immediate hazard to subjects or for other inevitable medical reasons, the investigator shall document all such deviations, including the reasons thereof, and immediately submit the documentation to the sponsor and to the IRB if required.

I. Concomitant Medications

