Demographic and subject characteristics will be summarized using descriptive statistics. Assessments that are measured on a continuous scale will be summarized descriptively using the mean, standard deviation, median, minimum, and maximum value by time. Variables that are measured on a categorical scale will be summarized as a proportion of the population.

The change from baseline will be summarized for effectiveness outcome assessments in common between subjects/sites and 95% confidence intervals constructed.

Adverse events will be summarized using MedDRA categories and by severity and relationship. Concomitant medications will be summarized by WHODrug categories.

C. Adverse Events

All adverse events will be coded according to Medical Dictionary for Regulatory Activities (MedDRA). Safety assessments will include treatment-emergent adverse events (TEAEs; adverse events that occur in subjects who undergo treatment). Subjects with TEAEs will be summarized with frequencies and percentages by system organ class and preferred term, severity, and relationship to treatment for each treatment group. Treatment-related adverse events will be defined as adverse events with investigator assessment of related or possibly related. In summaries of TEAEs by severity and relationship to study device, subjects reporting multiple episodes will be counted once under the worst severity and the strongest relationship, respectively. Serious Adverse Events will also be presented by relationship to treatment.

The number of subjects with at least one adverse event will be tabulated. The number of adverse events will also be tabulated. The number of subjects and the number of adverse events will be tabulated by severity and relationship.

D. Sample Size

This is an open-label, non-controlled study with no formal hypothesis testing planned. It is anticipated that up to 300 subjects will be enrolled in this study. Data from this study will be included in a patient registry. The statistical analysis plan for the patient registry will fully describe the methods used to evaluate data from this study.

VII. INFORMED CONSENT

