#### **Assessment of Compliance and DC packs**

##### **Compliance (Yes or No)**

##### **Total number of pack provided**

##### **Provant Device Return (End of Treatment Visit)**

Edema Evaluation at treatment site

- Mild, Moderate, Severe
- Pitting: Non-pitting, 1+, 2+, 3+, 4+, Lymphedema

Weight (End of Treatment Visit)

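### The SAP adverse event tables omit the event counts the protocol requires, and no described table summarises the device exposure actually received

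*SAP*

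**What the plan says.** **Adverse events, protocol.** Section III.C makes the main presentation subject-based and adds that "the number of adverse events will also be reported". Section VI.C repeats this and goes further: "The number of subjects and the number of adverse events will be tabulated by severity and relationship". Section VI states that its methods are the basis for the SAP.

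**Adverse events, SAP.** Section 11.1.2 sets the unit: "The number and percentage of subjects experiencing AEs will be summarized by system organ class and preferred term". Section 11.1.2.1 adds that "multiple occurrences of the same preferred term for a subject within a period will be counted only once". Sections 11.1.2.2 and 11.1.2.3 place each subject at the maximum severity and at the strongest relationship. The discontinuation and serious-event tables follow the structure of Table 14.3.1.1. Listing 16.2.12 holds the individual events.

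**Exposure, protocol.** Under section IV.G, staff assess adherence at interim visits and at completion by "reading and recording the number displayed on the study device usage meter". The meter starts at 0.0 and advances 1.0 per hour of treatment. Returned unused covers are also counted, and each session uses one cover.

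**Exposure, SAP.** For Table 14.2.1, section 10.1 says: "The frequency of treatment and length of the individual treatment sessions will be summarized using counts and percentages". Section 3.2.1 defines those two items as the treatment regimen recorded at baseline, with as-needed use among the options. Section 3.2.2 holds a yes/no compliance item and the number of packs provided. The usage meter is not mentioned anywhere in the SAP text.

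**The concern.** The device is self-applied, repeatedly, for up to 20 weeks. For such a device, how often a reaction occurs and how much treatment was delivered are central to reading the safety data. If only affected subjects are tabulated, a subject with one recorded skin reaction and a subject with many contribute the same entry. If only the prescribed regimen is tabulated, a low percentage of affected subjects cannot be told apart from little use of the device. An as-needed prescription says nothing about hours of use.

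The two halves differ in standing. The event count is an explicit protocol requirement that the SAP text does not carry through. The exposure summary is not asked for in protocol section VI; there, collected data simply go unused in the tables.

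**Working it through.** The plan gives no adverse event rate and no exposure figure, so there is nothing of its own to reproduce. The check is a comparison of texts, followed by an illustration of scale.

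**1. Event counts: requirement against output**

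- Number of events overall: required in Protocol III.C and VI.C; no column or table described in SAP 11.1.2.1.
- Number of events by severity: required in Protocol VI.C; SAP 11.1.2.2 gives subjects at maximum severity only.
- Number of events by relationship: required in Protocol VI.C; SAP 11.1.2.3 gives subjects at strongest relationship only.
- One SAP sentence, at the end of 11.1.2.1, says that incidence will be given as counts and percentages. It follows directly on the once-per-subject rules and names no event column, so it does not supply the missing count.
- SAP 3.2.3 collects a frequency field (single continuous, or recurrent/intermittent). No described table uses it.

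**2. What the subject count can hide (assumed inputs)**

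Assume 5% of subjects have a given reaction, with 1, 3 or 10 separately recorded episodes each. Events = affected subjects × episodes.

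- N = 200 (SAP): 0.05 × 200 = 10 subjects, shown as 10 (5.0%). Events: 10, 30 or 100.
- N = 300 (protocol): 0.05 × 300 = 15 subjects, shown as 15 (5.0%). Events: 15, 45 or 150.

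**3. Range of exposure from dispensed covers**

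Protocol IV.B dispenses up to 120 covers in packs of 30; the preset session is 30 minutes (0.5 h). Ceiling in hours = covers × 0.5.

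- One pack: 30 × 0.5 = 15 h.
- Full supply: 120 × 0.5 = 60 h.
- Ratio: 60 / 15 = 4.

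These are supply ceilings, not observed use.

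**4. Effect on a rate (assumed inputs)**

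Take N = 200, 10 affected subjects with 3 recorded episodes each (30 events), and 120 covers for every subject. Full use is 200 × 60 = 12,000 h. Rate = 1,000 × events / hours.

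- 100% use: 30 / 12,000 h = 2.5 per 1,000 h.
- 75% use: 30 / 9,000 h = 3.3.
- 50% use: 30 / 6,000 h = 5.0.
- 25% use: 30 / 3,000 h = 10.0.

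The described adverse event tables and Table 14.2.1 would be the same in all four cases.

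**The case against.** The strongest reply is that the SAP's counting rule is right. Protocol III.C makes the primary presentation subject-based, and VI.C itself counts a subject with multiple episodes once, at worst severity and strongest relationship. That stands: the rule should stay, and the defect is only the absent event count beside it.

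Several stronger readings are tempting but not supported:

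- *A reader might infer that repeated reactions and actual use are lost altogether.* They are not. Listing 16.2.12 shows individual events, Listing 16.2.8 is to hold all recorded treatment information, and SAP section 7 lists all study data. The gap is in the tables. For the meter, a place in a listing is only implied, since the SAP never names it.
- *A reader might infer that ten recurrences would always appear as ten events once a column is added.* The frequency field allows a recurring reaction to be recorded as one event, so the column alone may not show recurrence.
- *A reader might infer a range wider than 4-fold.* Twice daily for 20 weeks would be 280 sessions, but that exceeds the 120 covers and needs a resupply that the protocol does not describe.
- *A reader might argue that the SAP's on-study duration inflates treatment time by the three-month call.* The SAP schedule ends at the End of Treatment Visit and contains no such call, and no adverse event table uses that duration as a denominator.
- *A reader might treat the exposure summary as a dropped protocol analysis.* Protocol section VI does not ask for one. The protocol's remark about rare events over two million treatments is background, not a planned comparator.

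Finally, SAP section 13 refers to an index of tables and listings that is not in the text available. A table named only there cannot be excluded.

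**Conclusion.** The point holds in two parts of unequal weight.

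First, the SAP text omits a tabulation that the protocol requires: number of events, overall and by severity and relationship. This rests on direct comparison of the two documents, subject to the unseen index. The size depends on recurrence, which the documents do not give. Under the assumed 1 to 10 recorded episodes per affected subject, one subject row is compatible with a 10-fold range of events.

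Second, no described table summarises treatment received, although the meter and cover data that would show it are collected. The documents support a 4-fold range in supply (15 to 60 h) at 30 minutes per session; the rates per 1,000 h are illustrations only. This part is a worthwhile improvement, not a protocol departure.

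Neither part affects a formal test, since none is planned. Both should be settled before the tables are programmed.

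**What to change.** 1. **Event counts.** Keep the once-per-subject rule. In Tables 14.3.1.1 to 14.3.1.3, add a number-of-events column beside the subject count and percentage: overall, by severity and by relationship. Tabulate the single/recurrent frequency field as well, because a recurring reaction may be one record.

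2. **Exposure.** Keep the yes/no compliance item. Add recorded usage-meter hours and covers used to SAP 3.2.2 and Table 14.2.1. Covers used should be the number actually dispensed minus the number returned; Protocol IV.B allows up to 120, whereas IV.G writes the dispensed total as 120. Show device-related events per 1,000 meter-hours as a descriptive supplement. Do not convert hours to sessions by dividing by 0.5: the SAP allows 15-minute sessions, and the device can be stopped early.

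3. **Data handling.** Flag missing meter readings and readings from replaced devices. Confirm that the case report form captures the meter reading, since the SAP does not list it. Reconcile the protocol synopsis, which describes adherence as assessed verbally, with section IV.G.

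The cost is SAP wording and a few table columns, drawn from data the protocol already has sites collect. If the appendix index already names an event-count table, part 1 reduces to describing it in section 11.1.2.
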